11.5.2 Subject Disposition

A summary of all consented subjects will be provided. This will include a summary of subjects who consented, were enrolled, treated, completed study participation, discontinued study participation (including reasons), died, were lost to follow-up or withdrew consent. These summaries will be presented in the form of a CONSORT diagram.

11.5.3 Baseline Subject Characteristics

A summary of subject demographic, socioeconomic, and disease-related factors will be completed and selected subject medical history will be assessed.

11.5.4 Primary Analysis

The frequency and proportion of subjects alive at 6 months or better will be calculated for each study arm. Corresponding 95% confidence intervals will be estimated using the Clopper-Pearson method. A

two-sided test for binomial proportions will be carried out, testing the null hypothesis that there is no difference in the OS6 rate between the arms.

Poisson regression analyses will be used to analyze acute care utilization visits. Treatment arm will be included in the model as the primary covariate and an asymptotic test of significance will be carried out to compare acute care utilization between the arms.

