4. SUBJECT ALLOCATION

4.1 Randomization

Following informed consent and eligibility check per standard operating procedures, subjects will be randomized in a 1:1 fashion to either Arm A (standard of care plus ONN service) or Arm B (standard of care only) and assigned a Sequence Number. This will be accomplished utilizing the CTMS whereby a list of Sequence Numbers and associated treatment arm assignments randomly generated prior to study activation will be uploaded by a member of the Levine Cancer Institute Data Coordinating Center. The Sequence Number will be a four digit randomly generated ID number, ranging from 0001 to 9999. A stratified block randomization will be utilized including the following stratification factors to reduce confounding of comparisons between the treatment arms:

- COVID-19 study period:
 - Time from study activation to end of pandemic* (Study Period A)
 - End of pandemic to end of study (Study Period B)
 - Note: The time of the start of the post-pandemic era will be determined by a declaration from World Health Organization, Center for Disease Control (or other United States federal agency), or LCI, whichever comes first.

*On January 30, 2023, the Biden Administration announced its plan to end the COVID-19 national emergency and public health emergency in the United States on May 11,

2023. The end of the pandemic will be defined by the United States declaration of the end of the COVID-19 national emergency and public health emergency.

- Disease diagnosis:
 - Metastatic pancreatic
 - Locally advanced unresectable pancreatic
 - Metastatic or unresectable esophageal, gastroesophageal junction (GEJ) or gastric cancers
 - Metastatic or unresectable hepatocellular carcinoma
 - Metastatic or unresectable biliary cancer
 - Colorectal cancer patients who had disease progression on or are intolerance to fluorouracil, oxaliplatin, and irinotecan-based therapy

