11.2 Sample Size

This study is designed with co-primary objectives to evaluate the acute care utilization and 6-month OS rate. Power and sample size calculations were primarily calculated based on the OS landmark objective. The overall type I error rate for this study is alpha = 0.05. Therefore, the co-primary endpoints were both powered at the 2-sided alpha = 0.025 significance level. We estimate that treatment with standard therapy results in median survival of 8 months. Assuming an exponential distribution, this corresponds to a 6-month survival rate of approximately 60%. Therefore, the primary OS objective of this study is designed to test the null hypothesis that the 6-month OS survival rate is \leq 60%. A total of 300 evaluable subjects enrolled in a one-to-one fashion will provide 80% power, assuming the true 6-month OS rate with Nurse Navigation is 80%. A total of 347 subjects may need to be enrolled to achieve 300 evaluable subjects. A 20% improvement in the 6-month OS rate is considered clinically relevant. This sample size will also provide at least 93% power to detect a 20% reduction in acute care visits (assuming there will be 6 acute care utilization visits per year in the control arm).

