11.5.5 Secondary Analysis

Overall survival will be analyzed using Kaplan-Meier techniques. Tests of statistical significance between the arms will be carried out using the log-rank test. The 12-month survival rate will be estimated for each study arm based on the Kaplan-Meier estimates. A statistical test of significance will be carried out to compare the 12-month survival rates between the arms. This will be accomplished by pooling the standard errors of the 12-month OS rates and performing a Chi-Square test. Additional survival analyses and analysis of time from hospice referral to death will be conducted using Cox-proportional hazards models. Thirty-day readmissions will be analyzed using Poisson regression. Length of stay and adherence to clinical care will be analyzed using analysis of variance techniques. The frequencies and proportions of subjects referred to Supportive Oncology services will be calculated, alongside corresponding 95% confidence intervals estimated using the Clopper-Pearson method.

The following models will be estimated for each of the six multi-scale measures, thirteen single-item measures, and one average overall standardized score: Linear mixed models for repeated-measures will be used to analyze subject-level satisfaction as assessed through the derived endpoints of the EORTC IL109 customized questionnaire. Fixed factors included in the models will be treatment arm, sampling time (T1 and T2) and the treatment by time interaction. A random factor for subject will be included in the models to account for repeated observations on the same subject. For single-item measures, mixed-effects models for repeated ordinal outcomes will be estimated for the thirteen single-item measures using ordinal logistic regression. The response outcome may be treated as a 5-level raw score or a collapsed version (e.g., 2-level factor as raw scores 1-3 versus 4-5) as appropriate. Similarly, fixed factors included in the models will be treatment arm, sampling time (T1 and T2) and the treatment by time interaction, and a random factor for subject will be included in the models to account for repeated observations on the same subject.

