Using the models described above, univariate and multivariable modeling will be conducted to identify baseline prognostic factors and to estimate adjusted between-arm treatment effects. All models will be stratified including the stratification factors used in the randomization. Univariate models will be used to identify baseline factors (including subject demographic, socioeconomic, and clinical characteristics) that are individually prognostic. Statistically significant factors identified from the univariate models will then be jointly included in a multivariable model. Backwards elimination will be used to identify baseline factors that are independently prognostic. If it is determined that the sample sizes in some stratification strata are too sparse, then strata will be combined prior to analyses. This will result in a smaller number of strata, each with larger sample sizes.

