11.5.8 Interim Analysis

After 100 subjects have been enrolled in the OS evaluable population, a formal interim analysis will be conducted. The interim analysis is designed primarily to assess futility regarding the 6-month OS rate objective and will be based on the conditional power. If the conditional power falls below 50%, the OS6 objective may be removed from the co-primary objective. If this occurs, the primary objective will be based only on the acute care utilization objective. With this revised design, 158 evaluable subjects would provide 90% power to detect a 20% reduction in acute care utilization from 6 visits per year in the non-navigation arm based on a 2-sided alpha = 0.05 significance level.

If the OS6 conditional power is greater than 50% but less than 80%, the sample size may be increased so that the power for the revised sample size is maintained at 80%. As discussed in Chen et al, 2004, this sample size re-estimation will not inflate the type I error.

Sample size re-estimation

As per protocol, the interim futility analysis occurred on 9/22/2022. Based on the results of the interim analysis and on the initial statistical design, the trial will proceed with OS6 and ACU as co-primary

endpoints. In order to retain 80% power for the OS6 objective, the sample size will be increased from 107 evaluable subjects per arm to 150 evaluable subjects per arm.

In order to achieve a total of 300 evaluable subjects, it is estimated that approximately a total of 347 subjects may be enrolled.

Additionally, ~~an~~ interim efficacy analysisanalyses will be performed after 85 and 120 deaths in the evaluable population have occurred (Interim Efficacy Analysis I and II). This will be conducted under the auspices of the LCI DSMC and will be blinded to the Sponsor-Investigator and the study conduct trial site. If, in the clinical judgement of the LCI DSMC, there are impelling favorable OS trends, the study may be terminated due to ethical considerations. No formal statistical stopping rules will be utilized, and no alpha spend will be incurred due to this interim efficacy evaluation.

As per protocol, Interim Efficacy Analysis I occurred on 1/23/2022. Based on the results of the blinded survival analysis and the updated statistical design (following the interim futility analysis on 9/22/2022), the trial will continue and Interim Efficacy Analysis II will be performed after 120 deaths in the evaluable population have occurred.

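### The co-primary six-month survival test ignores the randomisation strata, and no interval for the between-arm difference is planned: a small efficiency and reporting point

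*Combined protocol and SAP*

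**What the plan says.** Section 4.1 states the design and its purpose: "A stratified block randomization will be utilized including the following stratification factors to reduce confounding of comparisons between the treatment arms". The factors are COVID-19 period (two levels) and diagnosis (six levels), so there are up to 12 cells.

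Section 11.2 says of the error rate: "Therefore, the co-primary endpoints were both powered at the 2-sided alpha = 0.025 significance level". It sizes the trial mainly on OS6, with about 60% alive at six months in the control arm and "assuming the true 6-month OS rate with Nurse Navigation is 80" per cent.

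Section 11.5.4 gives each arm's OS6 proportion with a 95% Clopper-Pearson interval, followed by a "two-sided test for binomial proportions will be carried out, testing the null hypothesis that there is no difference in the OS6 rate". No stratification factor is named. For acute care utilisation (ACU), the other co-primary endpoint, it specifies a Poisson regression and names treatment arm as the only covariate.

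Section 11.5.5 says of overall survival: "Tests of statistical significance between the arms will be carried out using the log-rank test". Later, in the paragraph on prognostic-factor modelling, it adds: "All models will be stratified including the stratification factors used in the randomization". It then allows pooling: "If it is determined that the sample sizes in some stratification strata are too sparse, then strata will be combined prior to analyses". No cell-size threshold or order of merging is given.

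**The concern.** When randomisation is balanced within groups that differ in prognosis, part of the outcome variation can no longer produce a chance difference between arms. A crude two-proportion test still counts that variation in its standard error. Its true type I error then falls below the nominal level, and some power is lost. A test stratified by the same factors recovers both.

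The sentence on stratified models does not settle the matter. It belongs to the secondary analysis and refers to models, whereas OS6 and the log-rank comparison are tests. As written, Cox models for survival would be stratified but the co-primary OS6 comparison would not. The sentence arguably reaches the ACU Poisson model, but section 11.5.4 does not say whether the primary ACU fit is the stratified one. Wherever strata are used, the open-ended permission to combine them leaves a choice that could move a p-value.

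The missing interval is a separate matter. The quantity tested at 0.025 is a difference between arms, and readers will want its size with an interval at the matching level.

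**Working it through.** **Inputs from the documents.** OS6 60% (control) versus 80% (navigation), two-sided alpha 0.025 (section 11.2); 107 and then 150 evaluable per arm (section 11.5.8); 347 enrolled to yield 300 evaluable, so 47/347 = 13.5% not evaluable; 2 × 6 = 12 cells (section 4.1).

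**Assumptions, because the documents are silent.** Diagnosis shares 30/10/20/10/15/15%; two COVID periods of equal size with no effect of their own; permuted blocks of 4 or 6. Control OS6 by diagnosis is one of three sets, each calibrated to a 60% average: all 60%; moderate spread, 48/62/62/66/64/70%; wide spread, 38/66/62/72/70/80%. The navigation effect is a common odds ratio.

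**Step 1: the plan's power figure.** Let z = 2.241, d be the difference and p̄ the mean rate. Then power = Φ{[d − z√(2p̄(1−p̄)/n)] / √[(p₁(1−p₁)+p₂(1−p₂))/n]}.
- n = 107: (0.20 − 2.241 × 0.0627)/0.0611 = 0.974, power 83.5%. Subtracting a continuity correction of 1/n gives 79.4%, in line with the stated 80%.
- n = 150: (0.20 − 2.241 × 0.0529)/0.0516 = 1.576, power 94.3%. The stated 80% does not follow from 60% versus 80% at this size.
- n = 150 with power 80%: the difference is 16.5 points (60% versus 76.5%).

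The comparison is therefore made at both 80% and 76.5%.

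**Step 2: why the crude test is conservative.** Let f be the share of outcome variance lying between diagnosis groups. With exact balance the true variance of the difference is (1−f) times the one the test uses, so type I error ≈ 2[1 − Φ(2.241/√(1−f))].
- Moderate: f = (0.30×0.12² + 0.10×0.02² + 0.20×0.02² + 0.10×0.06² + 0.15×0.04² + 0.15×0.10²)/0.24 = 0.0065/0.24 = 0.027, type I error 0.023.
- Wide: f = (0.30×0.22² + 0.10×0.06² + 0.20×0.02² + 0.10×0.12² + 0.15×0.10² + 0.15×0.20²)/0.24 = 0.0239/0.24 = 0.100, type I error 0.018.

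**Step 3: simulation, crude test versus 12-cell CMH.** There were 200,000 trials per setting. Ranges cover both block sizes and two exclusion settings: 300 randomised with none excluded, and 347 randomised with 47 excluded at random.

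| Control OS6 by diagnosis | Type I error, crude / CMH | Power at 60% v 80%, crude / CMH | Change at 60% v 76.5% |
|---|---|---|---|
| No spread | 0.025 / 0.025 | 94.3–94.4% / 94.1–94.3% | −0.4 to −0.1 |
| Moderate | 0.023 / 0.024–0.026 | 94.6% / 94.7–94.9% | +0.4 to +0.7 |
| Wide | 0.018–0.020 / 0.024–0.025 | about 95.0% / 96.0% | +2.6 to +2.7 |

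Merging the COVID periods (six strata) cuts the no-spread loss at 60% versus 80% to at most 0.1 point. A separate simulation with other shares and control rates as wide as 38–87% gave gains of 0 to about 1 point at 80% and 0 to about 4 points at 60% versus 76.2%.

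**Step 4: the interval.** At exactly 60% versus 80%, the standard error is √[(0.24+0.16)/150] = 0.0516, so the 97.5% interval is 20 ± 2.241 × 5.16 = 8.4 to 31.6 points. Per-arm intervals do not convey this. Take 90/150 versus 109/150. The test gives z = 2.32, p = 0.020, significant at 0.025. The two 95% Clopper-Pearson intervals, 51.7–67.9% and 64.8–79.6%, overlap. The 97.5% interval for the difference is 12.7 ± 2.241 × 5.41 = 0.5 to 24.8 points and excludes zero. The same conflict occurs for every count from 109 to 113 in the navigation arm.

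**The case against.** A pre-specified unadjusted two-proportion test is legitimate, and its error here is on the safe side. At 60% versus 80% the two tests reach different decisions in only about 0.4% to 1.0% of simulated trials. The larger gain needs both a wide spread between diagnoses and a smaller effect than the protocol states, and neither is in the documents. Section 11.5.5 already promises stratified models, adjusted effects and pooling of sparse strata. All of this stands, and it is why the point is minor.

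The stronger objection concerns timing. Section 11.5.8 records: "As per protocol, the interim futility analysis occurred on 9/22/2022". That look used OS6 and led to the increase from 107 to 150 per arm. Changing the final statistic afterwards separates it from the one in force when that decision was taken, and the simulations above are of a fixed design with no interim look. Blinding of the Sponsor-Investigator is stated for the efficacy looks but not for the futility look. These facts do not rule the change out. They do mean that who makes it, and when, must be documented, and that the crude result should be kept.

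Section 3.2 also admits borderline resectable pancreatic and small bowel cancers, which have no named stratum in section 4.1, and section 4.1 describes the end of the pandemic in more than one way. Every subject was nonetheless assigned to a stratum at randomisation, and that assignment can be used. Finally, an interval for the difference could be computed from the reported counts. Planning it costs nothing and does not depend on which test is primary.

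**Conclusion.** The point holds as one to consider; validity is not at risk. Three statements rest on the text alone: the OS6 and log-rank tests are unstratified after stratified randomisation, it is unclear whether the primary ACU model is stratified, and no interval for the OS6 difference is planned. The size of the efficiency loss rests on assumed stratum rates, shares and block sizes. On the main assumptions, the crude test's type I error is 0.018 to 0.025 against a nominal 0.025. Stratifying changes power by about −0.2 to +1.0 points at the design effect and by −0.4 to +2.7 points where crude power is about 80%. The gain is real only if diagnosis is prognostic for six-month survival. The 5-year stage IV survival figures in section 1.1.2 (3% pancreatic, 5–10% gastroesophageal, 14% colorectal) make that plausible but do not establish it at six months.

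**What to change.** In section 11.5.4:
1. Test OS6 with a CMH test over the randomisation factors, using the stratum recorded at randomisation, at two-sided alpha 0.025. Keep the crude two-proportion test as a sensitivity analysis.
2. Fix the pooling rule on counts combined over arms. For example, merge the two COVID periods first, then merge any diagnosis group with fewer than 10 evaluable subjects into a group named in advance.
3. Report the stratified risk difference with a 97.5% interval, naming the weights and the variance method. The per-arm 95% Clopper-Pearson intervals can stay as description.
4. State that the primary ACU Poisson model includes the same factors.

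In section 11.5.5, make the log-rank test stratified.

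Because the futility look has already taken place, staff who have not seen outcomes by arm should make and date the amendment. The cost is SAP wording and a few lines of code, with no new data. If diagnosis proves not to be prognostic, the price is about 0.1 to 0.2 power points at 60% versus 80%. If the primary test is left as it is, the interval in item 3 and a statement of which primary analyses the stratification sentence covers are still worth adding.

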1.1.4 Acute Care Utilization

Certain populations are more likely than others to use acute care services for cancer-related symptoms. A 2018 study showed that pancreatic and gastric cancer patients were more likely than not to be frequent emergency department (ED) attenders (22). In addition, a study of advanced cancer patients showed that those who missed their first appointment were more likely than patients who kept their appointment to have an ED visit within two weeks of the missed appointment (23). These studies suggest that certain patient groups especially need additional support to ensure that they get appropriate care when they need it, outside of the acute care setting. Initiatives to enhance care coordination and easy access to care may help to keep patients out of the ED, improve the quality of cancer care, and alleviate the high economic burden of ED attendance and frequent hospitalization on the healthcare system.

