11.3 Endpoints

11.3.1 Definition of Primary Endpoints

Overall survival at 6 months (OS6) will be determined as a binary variable indicating whether or not the subject was alive at 6 months following randomization.

Acute care utilization visits will be calculated for each subject as the total number of acute care visits normalized to an annual basis. Acute care visits will include unplanned hospital admissions, ED visits, and urgent care visits.

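### The acute care co-primary puts an annualised visit count into plain Poisson regression with no exposure offset or overdispersion term, so its 0.025 level is not secured

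*Combined protocol and SAP*

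**What the plan says.** Section 11.3.1 (Definition of Primary Endpoints) sets the endpoint: "Acute care utilization visits will be calculated for each subject as the total number of acute care visits normalized to an annual basis". It adds: "Acute care visits will include unplanned hospital admissions, ED visits, and urgent care visits". It gives no rule for an ED visit that ends in admission.

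Section 11.5.4 (Primary Analysis) sets the model: "Poisson regression analyses will be used to analyze acute care utilization visits". Arm is the main covariate, and "an asymptotic test of significance will be carried out to compare acute care utilization between the arms". No section names an exposure offset, a dispersion parameter, a negative binomial model or a robust variance. Section 11.5.5 says that models are stratified by the randomisation factors.

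Section 11.2 (Sample Size) sets the level: "the co-primary endpoints were both powered at the 2-sided alpha = 0.025 significance level". On power it says: "This sample size will also provide at least 93% power to detect a 20% reduction in acute care visits", with 6 visits per year in the control arm. It states no follow-up length and no dispersion.

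Exposure differs between subjects. Section 5.4 ends ACU collection at off-intervention, which under section 8.1 includes stopping all anti-cancer therapy. Section 11.4 keeps subjects who die within six months in the evaluable population. Section 11.2 plans on median control survival of 8 months: "Assuming an exponential distribution, this corresponds to a 6-month survival rate of approximately 60" per cent.

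**The concern.** Poisson regression takes the variance of an observed count to equal its mean. An annualised value is not an observed count: two visits in one month become 24 per year, and the model credits that subject with the information of 24 visits. The standard error is then wrong even if visits are perfectly Poisson.

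The text also allows a kinder reading, in which the scaling is done through a log-time offset. That cures the exposure problem but still requires visits to vary no more between subjects than Poisson allows. Section 1.1.4 points the other way: "Certain populations are more likely than others to use acute care services for cancer-related symptoms". Counting an ED visit and the admission it leads to as two visits would also push the variance above the mean.

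ACU carries half of the trial's alpha. At stake is a false claim that navigation reduces acute care use, made more often than the stated 0.025 allows.

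**Working it through.** **Inputs.** Two-sided alpha 0.025 (z = 2.241), 6 versus 4.8 visits per year, 150 evaluable per arm (sections 11.2, 11.5.8). T is years of ACU exposure. Each subject's rate is the mean rate times a factor with mean 1 and variance k. The documents give neither the distribution of T nor k; every value below is an assumption.

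**1. The plan's own power figures.** Power = Φ(|ln 0.8| / √v − z), with v = [1/(6t) + 1/(4.8t) + 2k]/n.
- ACU-only design (section 11.5.8), n = 79, alpha 0.05, t = 1, k = 0: v = 0.375/79, power 90.0%. The plan says 90%.
- n = 107, alpha 0.025, t = 1, k = 0: v = 0.375/107, power 93.7%. The plan says at least 93%.
- n = 150, same assumptions: v = 0.375/150, power 98.7%.

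So the stated power rests on one full year per subject and variance equal to mean, and the 93% matches the superseded 107 per arm.

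**2. Literal reading: annualised count as response.** With visits Y and R = Y/T, Var(R) = 6·E[1/T] + 36k. Dividing by the mean of 6, the true variance is E[1/T] + 6k times the assumed one. The actual level is 2Φ(−2.241/√(E[1/T] + 6k)). A factor of 1.31 gives 2Φ(−1.958) = 0.05, twice nominal.

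Levels at k = 0 (formula or 10,000 simulated null trials; they agree within 0.01):

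| Assumed exposure | Level |
|---|---|
| 1 year each | 0.026 |
| 8 months each | 0.07 |
| 6 months each (E[1/T] = 2) | 0.11 |
| Uniform 6–12 months | 0.057 |
| Uniform 6–30 months | 0.012–0.014 |
| Exponential, 8-month median, 6–54 months potential follow-up, minimum 60–90 days | 0.11–0.15 |
| Same, minimum 7–30 days | 0.21–0.29 |
| Same, ONN at 80% six-month survival but no ACU effect, minimum 60–90 days | 0.08–0.11 |
| Same, minimum 7–30 days | 0.15–0.23 |

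**3. What planned survival alone implies.** Exposure cannot outlast survival. If a share p dies before six months, E[1/T] > 2p + (1 − p)/Tmax.

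| Tmax | p = 0.40 | Level above | p = 0.30 (ONN at 80%) | Level above |
|---|---|---|---|---|
| 12 months | 0.8 + 0.6 = 1.40 | 0.058 | 0.6 + 0.7 = 1.30 | 0.049 |
| 30 months | 0.8 + 0.6/2.5 = 1.04 | 0.028 | 0.6 + 0.7/2.5 = 0.88 | 0.017 |
| 54 months | 0.8 + 0.6/4.5 = 0.93 | 0.020 | 0.6 + 0.7/4.5 = 0.76 | 0.010 |

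The bound shows inflation when maximum exposure is about a year. With long maximum exposure it settles nothing.

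**4. Offset reading, plain Poisson variance.** With equal follow-up the variance factor is 1 + 6kT. At k = 0.25 it is 2.5 with one year each (level 0.156) and 1.75 with six months each (0.090). Across the simulated exposure patterns the level is 0.020–0.027 at k = 0, 0.05–0.12 at k = 0.1 and 0.08–0.24 at k = 0.25.

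If a share q of episodes are ED-to-admission pairs counted twice, variance/mean = (1 + 3q)/(1 + q). At q = 0.25 (assumed) this is 1.75/1.25 = 1.4, and the simulated level is 0.056–0.058 even at k = 0.

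**5. Offset with sandwich variance.** The level is 0.021–0.032 in every scenario. In a fitted model with six diagnosis strata (rate multipliers 0.6–1.5 assumed, 14-day minimum), the annualised response gave 0.24 and offset plus sandwich gave 0.026. Adding strata therefore does not repair the literal reading.

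**6. Power at 150 per arm for a valid test, equal follow-up.**

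| k | 6 months each | 1 year each |
|---|---|---|
| 0 | 82% | 98.7% |
| 0.1 | 71% | 91% |
| 0.25 | 58% | 75% |

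At k = 0, 93% needs 8.3 months each. With one year each, 93% holds up to k = 0.083.

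**The case against.** The strongest reply is that the plan is under-specified rather than wrong. Poisson regression is a count model, annualising is compatible with a log-time offset, and on that reading with k = 0 the level is nominal. The largest figures need annualised values entered as if they were counts, and very short minimum exposures that the documents do not state. The survival bound shows no inflation at a 54-month maximum, and uniform 6–30 months is conservative, so even the direction depends on assumptions. Diagnosis strata might absorb some between-subject variation under the offset reading. At least 93% is true as a lower bound on a one-year Poisson basis. Robust variance on the annualised response would keep the endpoint as defined.

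Much of this stands. The magnitudes are not fixed by the documents, the survival bound is weak for long exposure, and no stratified plain-offset result was computed. Robust variance on the annualised response does hold the level (0.024–0.030 in simulation), so the offset is not the only valid repair. None of this secures 0.025. The literal reading needs E[1/T] + 6k near or below 1. The offset reading needs residual dispersion close to nil. The plan states neither condition and has no safeguard if it fails.

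**Conclusion.** The concern holds. As written, the ACU analysis has no term that protects its 0.025 level against unequal exposure or overdispersion. On the literal reading, simulated levels without overdispersion run from 0.012 (conservative) to 0.29 over the exposure patterns tabulated, with 0.11 at six months each. On the offset reading the level is nominal at k = 0 and 0.05–0.24 for k between 0.1 and 0.25. Confidence is high that the level is not secured; its actual value rests on assumed exposure and k. The stated ACU power likewise rests on an unstated full year per subject and no overdispersion, which sits poorly with a planned median survival of 8 months.

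**What to change.** Before the primary analysis, amend three places.

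- **Sections 11.3.1 and 11.5.4:** model the raw visit count with log(observed ACU time at risk) as offset, by Poisson regression with sandwich variance or by negative binomial regression, with arm and the randomisation strata. Report the rate ratio with a 97.5% confidence interval. If the mean of per-subject annualised rates is the intended quantity, keep it and specify robust variance for that response.
- **Section 11.3.1:** state whether an ED visit that ends in admission counts once or twice.
- **Section 11.2:** restate ACU power for 150 per arm with its follow-up and dispersion assumptions. k can be estimated from blinded pooled ACU data.

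The cost is wording only. The offset model estimates visits per person-time, so longer-followed subjects weigh more than in a mean of annualised rates. The stated ACU power may become less favourable. No extra patients are needed, because the trial is sized on six-month survival.
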